**Figure 3. Anatomic Target of Superior Laryngeal Nerve Blocks.**

During the procedure, the thyroid cartilage, hyoid, and thyrohyoid membrane are palpated as key anatomic landmarks. The target of the injection, the superior laryngeal nerve, pierces the thyrohyoid membrane superior to the superior laryngeal artery. The plunger is drawn back prior to injection to ensure needle tip is not intravascular. Illustration by author.

Patients will be provided a log to track their progress throughout treatment. This will include a visual analogue scale to be completed daily after each injection to document cough severity, as well as opportunities to document any adverse effects or general comments. An example of this log can be seen in Figure 4. At each follow up visit, patients will provide a dichotomous answer (Yes or No) if they experienced improvement in cough and will disclose how long the improvement lasted. They will also fill out the Leicester Cough Questionnaire (LCQ), a validated 19-question quality of life survey for chronic cough. The LCQ will be the study's primary outcome measure. Please see Appendix 1 for a copy of the Leicester Cough Questionnaire. After the last injection, patients will return to the clinic in three months or opt to be contacted via telephone to assess if symptoms have returned.

Date of last injection: _____
 
WEEK 1  Please mark on the line below with a "X" how severe you believe your cough is. The far left indicates no cough at all, and the far right is indicative of the most severe cough.
 
Day 1 no cough ..... severe cough
 
Day 2 no cough ..... severe cough
 
Day 3 no cough ..... severe cough
 
Day 4 no cough ..... severe cough
 
Day 5 no cough ..... severe cough
 
Day 6 no cough ..... severe cough
 
Day 7 no cough ..... severe cough
	

Date of last injection: _____
 
WEEK 2  Please mark on the line below with a "X" how severe you believe your cough is. The far left indicates no cough at all, and the far right is indicative of the most severe cough.
 
Day 1 no cough ..... severe cough
 
Day 2 no cough ..... severe cough
 
Day 3 no cough ..... severe cough
 
Day 4 no cough ..... severe cough
 
Day 5 no cough ..... severe cough
 
Day 6 no cough ..... severe cough
 
Day 7 no cough ..... severe cough
	

Any side effects?
	
Any side effects?


Additional comments?
	
Additional comments?

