#### 4.0 Study Endpoints (if applicable)

Primary study endpoints include improvement in cough, measured by dichotomous yes/no response to improvement, the Leicester Cough Questionnaire (LCQ), and a visual analogue scale for symptom severity. Due to its validation, the LCQ will be the primary outcome measure. Secondary study endpoints include the complication and side effect rate from the injections.

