### **Figure 2. Flow Diagram of Study Design**

Injection will be completed near the lateral thyrohyoid membrane by a single experienced laryngologist per previously published methodology utilizing bony, soft tissue and cartilaginous landmarks. An illustration of the anatomic target for the injection can be seen in Figure 3. To minimize patient discomfort, lidocaine cream will be applied to the skin prior to injections.

Following injection, patients will be instructed to follow up in a 2- to 3-week time frame; however, we will include all patients in analysis if they follow up within 1-4 weeks. Any follow up outside of that window will lead to removal of the patient's data from the analysis. At follow up, if the patient's cough has improved by greater than or equal to 50% compared to baseline, we will repeat the injection on the same side. If less than 50%, we will move to the other side to perform the injection. Patients will undergo a total of two injections before data collection is complete for analysis. If patients were to experience full resolution of cough (i.e. report 0/10 for cough severity) after the first injection alone, then at that point, their condition would be considered cured and their enrollment in the study will finish. The reason for this is to avoid unnecessary and unindicated injections in patients with resolution of cough.

2 weeks after the second injection, participants will be unblinded. If in the placebo group, they will have the opportunity to complete 2 additional treatment injections (unblinded) under the study protocol. Data will be collected and stored in the same fashion as prior to unblinding.

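### Improvement on the VAS is listed as an endpoint, but the available text specifies no VAS or other severity rating before injection 1

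*Combined protocol and SAP*

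**What the plan says.** **Endpoint.** Section 4.0 states: "Primary study endpoints include improvement in cough". It lists three measures of it: a yes/no answer, the Leicester Cough Questionnaire (LCQ) and a VAS for severity. The LCQ is then named as the primary outcome measure, and Section 10.0 repeats this.

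**When the VAS is taken.** Section 10.0, below the Figure 3 caption, says of the patient log: "This will include a visual analogue scale to be completed daily after each injection to document cough severity". The log is meant to run through treatment: "Patients will be provided a log to track their progress throughout treatment". The form itself is only illustrative: "An example of this log can be seen in Figure 4". It shows Week 1 and Week 2 with seven lines each, begins at Day 1 and has no line for a day before injection.

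**What happens before injection 1.** The only assessment that Section 10.0 lists at the initial visit before the injection is nasal laryngoscopy.

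**Follow-up.** After an injection, "patients will be instructed to follow up in a 2- to 3-week time frame". Visits at 1 to 4 weeks are accepted for analysis. Patients are unblinded 2 weeks after the second injection.

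**Use of a baseline.** The side of the second injection depends on whether "cough has improved by greater than or equal to 50% compared to baseline". No instrument is named. The same paragraph defines full resolution by a 0/10 severity report.

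**Analysis.** Section 12.0 plans a regression on the daily VAS, with no baseline covariate or change score stated.

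**The concern.** Improvement is a comparison with the state before treatment. A log filled in only after injection records how severe the cough is, not how much it has changed. If no rating is taken before injection 1, two things are lost for the VAS: each patient's change from baseline, and the option of adjusting the arm comparison for starting severity. Neither can be recovered once the first injection has been given. With 25 patients per arm, chance differences in starting severity can be appreciable, so adjustment is worth having.

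Two lesser matters sit beside this. The example form is shorter than most of the accepted follow-up window, so days close to a late visit may have no line. Those days bear on Aim 1c, the time at which symptoms return. Also, the 50% rule refers to a baseline that the available text neither records nor ties to a scale. The sample-size outcome in Section 6.0, more than 50% improvement, has the same gap.

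**Working it through.** **1. The plan's own figure.** The plan gives no calculation for the VAS. The nearest figure is Section 6.0's 18 per group for more than 50% improvement. I read 70% and 25% as the response rates in the two arms and the stated 80% as power. A two-sided 5% level is assumed, because none is given. With no continuity correction:

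n = [1.960 × √(2 × 0.475 × 0.525) + 0.842 × √(0.70 × 0.30 + 0.25 × 0.75)]² / (0.70 − 0.25)² = (1.384 + 0.531)² / 0.2025 = 18.1

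This rounds up to 19, and power at 18 per arm is 79.8%. The stated figure is reproduced to within one patient per arm. Nothing below changes it.

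**2. Is there a baseline VAS?**

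| Place | Content | Rating before injection 1 |
|---|---|---|
| Section 10.0, initial visit | Laryngoscopy, then injection | None listed |
| Section 10.0, patient log | VAS daily after each injection | None |
| Figure 4, example log | Day 1 to Day 7, two weeks | None |
| Section 10.0, follow-up visits | Yes/no answer, duration of improvement, LCQ | Not applicable |
| Section 12.0 | Regression on daily VAS | No baseline term |
| Figure 2 | Not shown | Unknown |

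**3. What adjustment would be worth.** Let r be the correlation between baseline VAS and a patient's follow-up VAS. The documents do not give it, so 0.5 to 0.7 is assumed. Relative to comparing follow-up VAS alone, adjustment for baseline multiplies the variance of the arm difference by 1 − r²:

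- r = 0.5: 1 − 0.25 = 0.75, a cut of 25%.
- r = 0.6: 1 − 0.36 = 0.64, a cut of 36%.
- r = 0.7: 1 − 0.49 = 0.51, a cut of 49%.

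In sample-size terms, 25 per arm with adjustment gives roughly the precision of 25/0.75 = 33 to 25/0.51 = 49 per arm without it. This ignores the degree of freedom spent on the covariate.

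A simple change score does less well. With equal variances its factor is 2(1 − r), which is 1.0 at r = 0.5 and 0.6 at r = 0.7. The baseline should therefore enter the comparison as a covariate, with change reported alongside.

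**4. Days without a line if only the example form is issued.** Uncovered days = max(0, visit day − 14):

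| Visit day | Uncovered | Share |
|---|---|---|
| 7 | 0 of 7 | 0% |
| 14 | 0 of 14 | 0% |
| 21 | 7 of 21 | 33% |
| 28 | 14 of 28 | 50% |

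Visits on days 15 to 21, inside the instructed window, leave 1 to 7 days. After injection 2 the 14 lines reach unblinding.

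**The case against.** The case on the other side has real force on several points.

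**Section 10.0 is not a full assessment schedule.** It lists no LCQ before injection either, yet Section 12.0 analyses LCQ changes, so a baseline LCQ is plainly intended. Figure 2 is not shown and may list baseline assessments. This stands as a limit: one can say only that the available text specifies no baseline severity rating, not that none will be taken. Unlike the LCQ, though, the VAS has no planned change analysis that would imply a baseline.

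**The VAS comparison survives.** A reader might infer that the VAS endpoint is unusable. It is not. Randomised arms can be compared on post-injection VAS, and a regression on daily values needs no baseline. What goes is within-patient change and precision. The LCQ is in any case the primary outcome measure.

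**The log is not said to stop at day 14.** A reader might take Figure 4 as an end date. The text calls it an example, asks for daily completion during treatment and gives no last day. Section 13.0 has the log reviewed at least every 4 weeks. The gap arises only if no further pages are issued and the visit falls after day 14. No distribution of visit days is given, so the number of patients affected is unknown. Return of symptoms is also asked about at each visit and at three months.

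**The 50% rule is not tied to the VAS.** A reader might infer that it fails, or rests on recall, because the log starts late. The rule names no instrument and may use the 0 to 10 report, which the site's earlier series also used. The gap is an undefined instrument and baseline, separate from when the log begins.

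**Conclusion.** The point holds in a limited form. Section 4.0 makes VAS improvement an endpoint, while the available text schedules the VAS only after injection and specifies no severity rating beforehand. Followed as written, VAS change cannot be calculated and the VAS regression cannot be adjusted for starting severity. The cost is precision and interpretability, not validity. About 25% to 49% of the variance of the arm difference is forgone if r lies between 0.5 and 0.7. That range is an assumption, and a single baseline mark may correlate less strongly than an average over several days would.

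The log-length gap is conditional: none up to day 14, one third of days at day 21 and half at day 28, if only the example form is used. The undefined baseline in the 50% rule is a matter for the sponsor to reconcile.

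The change is worth making because it is nearly free and a missed baseline cannot be recovered. It is not critical, since the primary outcome measure is the LCQ.

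**What to change.** **Section 10.0.** Add that every patient marks one VAS line, on the same scale as the log, after consent, before the allocation card is opened and before injection 1. One mark for everyone keeps the baseline equally precise across patients. Taking it before the card is opened keeps it free of any influence from the unblinded practitioner.

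**Section 12.0.** State that this mark is used to compute VAS change and is a covariate in the VAS regression.

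**Log.** Issue enough weekly pages to reach the follow-up visit. The latest accepted visit, day 28, needs (28 − 14)/7 = 2 pages beyond the example. This matters chiefly between injections 1 and 2, because after injection 2 the existing lines already run to unblinding.

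**50% rule.** The sponsor should reconcile the 50% wording, the 0/10 report and the severity scale in Section 10.0, so that the instrument and the recorded baseline are explicit. No instrument and no clinical rule is proposed here.

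**Cost.** One extra mark at the first visit and up to two extra log pages, with slightly more burden for patients whose visit is late. If Figure 2 already lists a baseline VAS, the first change reduces to repeating it in the text.

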Recently, we retrospectively reviewed our experience at the Medical University of South Carolina with in-office SLN blocks for the treatment of chronic neurogenic cough and our unpublished data are consistent with the work of Simpson, et al. and Dhillon. We found that within a cohort of 23 patients (4 males, 19 females, average age 63.6 years), 17 (74%) reported improvement with the injections, 2 (9%) reported initial improvement followed by return to baseline, and 4 (17%) did not have any improvement. The average number of SLN blocks performed per patient was 3.8. Of the 23 patients, 13 had recorded pre- and post-treatment Hull Cough Sensitivity Questionnaire scores and changes in scores were significantly improved from an average of 38 to 23 ( $p = 0.005$ ). All patients reported their symptom severity on a scale of 0-10 and there was a significant negative correlation between the number of injections and symptom severity scores with the largest difference following the initial injection (Figure 1). There were no major adverse events, however 4 patients (17%) reported self-limited post-injection globus sensation.

Although the current data support the efficacy and safety of SLN blocks for chronic neurogenic cough, there are no prospective investigations. Questions remain regarding safety and efficacy, particularly the potential for placebo effect, as well as proper medication dosing and timing. Our hypothesis is that superior laryngeal nerve blocks will provide significant improvement in cough severity compared to placebo. By better understanding the efficacy of superior laryngeal nerve blocks in the treatment of chronic cough, the care of patients presenting with this common symptom will be optimized.

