## 12.0 Data Management

Descriptional analysis of all demographic data, including sex and age, will be completed. Dichotomous data will be summarized as percentages per group per injection and compared via chi-squared analysis. Changes in Leicester Cough Questionnaire scores, both global and specific domains (physical, psychological and social), will be analyzed via a linear regression model. An independent t-test will then be used to compare both study arms. Regression analysis will also be performed on the data collected from the patient log, specifically the daily visual analogue scale. A ruler will be used to the identify the exact percentage along the scale that represents the patient's cough severity. A comprehensive compilation of side effects reported by the treatment group will be reported as a proportion of the total number of patients in the treatment study arm (n = 25) and compared to the placebo group (n=25). The data collected from the placebo group pre-unblinding will be directly compared to the results achieved from treatment injections offered following unblinding.

Data will not leave MUSC. Patient identifiers (MRN) will be kept coded on a separate, password-protected file stored on a secure drive.

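### The yes/no improvement endpoint fixes neither status at the visit nor a comparator, so relief that has ended can count as Yes and the answer after injection 2 is ambiguous

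*Combined protocol and SAP*

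**What the plan says.** Section 4.0 of the protocol lists three measures together: "Primary study endpoints include improvement in cough, measured by dichotomous yes/no response to improvement, the Leicester Cough Questionnaire (LCQ), and a visual analogue scale". It then ranks them: "Due to its validation, the LCQ will be the primary outcome measure". Section 10.0 repeats that ranking.

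The yes/no item is described in section 10.0, in the text after Figure 3: "patients will provide a dichotomous answer (Yes or No) if they experienced improvement in cough and will disclose how long the improvement lasted". No threshold, minimum duration, requirement that the improvement be present at the visit, or comparator is given.

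The analysis is in section 12.0: "Dichotomous data will be summarized as percentages per group per injection and compared via chi-squared analysis". The reported duration plays no part in it.

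Four other places bear on the point:

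- **Comparator.** Section 10.0 refers to baseline only in the rule for the side of the second injection: "if the patient's cough has improved by greater than or equal to 50% compared to baseline, we will repeat the injection on the same side". That reference is not attached to the yes/no item.
- **Timing.** On the visit window, section 10.0 says "we will include all patients in analysis if they follow up within 1-4 weeks".
- **Early exit.** Under section 10.0, a patient whose cough resolves fully (0/10) after injection 1 finishes the study and has no second injection.
- **Sponsor's series.** Section 2.0 reports 23 patients in three groups: 17 improved, 4 did not, and "2 (9%) reported initial improvement followed by return to baseline".

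**The concern.** An answer about improvement experienced, followed by how long it lasted, allows for improvement that is already over. A patient who felt better for a day and is back at baseline when seen, up to four weeks later, can truthfully say Yes. The planned chi-squared test then treats that patient like one who is still better.

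The arms may differ in how often this happens. The active syringe contains lidocaine and the placebo is saline, and sections 2.0 and 3.0 describe the block as an effective anaesthetic for awake intubation. Short-lived relief is therefore plausibly commoner on active treatment, whereas the trial's aim is treatment of chronic cough.

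The second difficulty is the reference after injection 2. Summarising by injection invites comparison with the state just before that injection. Comparison with the state before the study is equally natural. A patient who gained part of the way after injection 1 and stayed there would answer No on the first reading and Yes on the second. Patients who hold a gain are the ones this endpoint most needs to classify consistently.

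**Working it through.** **1. The sponsor's series (section 2.0).**

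- Improved: 17/23 = 73.9%, matching the stated 74%.
- Improved, then back to baseline: 2/23 = 8.7%, matching the stated 9%.
- Improved at any time: (17 + 2)/23 = 19/23 = 82.6%.
- Shift: 82.6 − 73.9 = 8.7 percentage points, or 0.087 × 25 = 2.2 patients in an arm of 25.

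The exact 95% confidence interval for 2/23 is 1% to 28%. The series is uncontrolled, averaged 3.8 blocks per patient, and gives no time of relapse. It cannot show how many would have relapsed within a 1-4 week window after one or two injections.

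**2. The plan's sample size (section 6.0), as a base for illustration.** Inputs are 70% against 25%. I read the 70% as the active response rate and the stated 80% as power, and I assume a two-sided alpha of 0.05, which the plan does not state.

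- Pooled formula, with mean proportion 0.475: n = [1.96 × √(2 × 0.475 × 0.525) + 0.842 × √(0.70 × 0.30 + 0.25 × 0.75)]² / 0.45² = 18.1, rounded up to 19 per arm.
- Arcsine formula: 17.95, rounded up to 18 per arm, which is the plan's figure.
- Power at the planned 25 per arm: 91.5%.

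These rates are for more than 50% improvement, which is not what the yes/no item asks. They serve only as a starting point.

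**3. Which way the difference moves.** Let a share t of patients without sustained response answer Yes because of brief relief. The documents give no value for t, so I take 0 to 0.4.

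- Active: 0.70 + 0.30 × t(active).
- Placebo: 0.25 + 0.75 × t(placebo).
- Change in the difference: 0.30 × t(active) − 0.75 × t(placebo).

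From this base, the difference is inflated only if t(active) is more than 0.75/0.30 = 2.5 times t(placebo). Otherwise it is unchanged or diluted.

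*Same t in both arms, 25 per arm:*

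| t | Active | Placebo | Difference | Power |
|---|---|---|---|---|
| 0 | 70% | 25% | 45 points | 91.5% |
| 0.1 | 73% | 32.5% | 40.5 points | 84% |
| 0.2 | 76% | 40% | 36 points | 75% |
| 0.3 | 79% | 47.5% | 31.5 points | 64% |
| 0.4 | 82% | 55% | 27 points | 54% |

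*Sustained response 25% in both arms, brief relief on active only, 25 per arm:*

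| t | Active | Placebo | Chance of a significant result favouring active |
|---|---|---|---|
| 0.1 | 32.5% | 25% | 8% |
| 0.2 | 40% | 25% | 20% |
| 0.3 | 47.5% | 25% | 38% |
| 0.4 | 55% | 25% | 59% |

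The nominal chance in that direction is 0.05/2 = 2.5%.

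**4. The comparator after injection 2.** Sections 10.0 and 12.0 were read together for a rule that settles it, and there is none. The exit rule removes patients with complete resolution after injection 1, so the ambiguity concerns partial improvers only.

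**The case against.** The strongest reply is that the information is already collected. Duration is asked with the yes/no answer, a visual analogue scale is filled in daily, the LCQ is completed at each visit, and there is a contact at three months about return of symptoms. Since Aim 1c is the time at which symptoms return, asking about any improvement and then its length looks deliberate. Transient responders could be identified from these data. That stands, but no planned analysis uses them to reclassify a Yes, and a rule written after the data are seen would be post hoc.

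It is also fair that section 10.0 describes the question and does not reproduce the visit form. The form may be clearer. If so, the protocol should state the form's definition.

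Two stronger readings are tempting and not supported:

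- A reader might infer that the trial's primary result is compromised. The LCQ is the designated primary outcome measure and does not depend on this item.
- A reader might infer that the treatment difference is inflated by about 9 points. That needs relapse within the trial's visit window and brief relief confined to the active arm. The documents give neither the relapse timing nor the duration of anaesthetic relief, and Aim 1b and the assumed 25% placebo improvement both anticipate placebo response.

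**Conclusion.** The point holds for one of three listed primary endpoints, not for the lead measure. As the plan stands, improvement that has ended can be analysed as Yes, and two patients with the same course can give different answers after injection 2. The sponsor's series shows that the distinction can matter (74% against 83%) and that the sponsor drew it in earlier work, but 2 patients out of 23 do not measure its size in this trial.

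The direction of any bias is open. The tables show that it could create an apparent benefit or hide a real one. They rest on assumed values of t, on an assumed two-sided alpha of 0.05, and on rates planned for a different responder definition. This is a cheap improvement in definition and does not invalidate the design.

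**What to change.** Define the endpoint item as current status against a fixed reference, for example: *Compared with before your first study injection, is your cough better now? Yes/No.* Ask it at each follow-up visit the patient attends and use that answer in the chi-squared comparison. A patient whose improvement has ended then answers No. Keep a separate descriptive item for Aim 1c: *Have you had any improvement since the last injection, and how long did it last?* State both in sections 10.0 and 12.0 before data are collected, since past answers cannot be reliably asked again.

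The cost is one reworded and one added question, with no extra visits. The reported response rate may be lower, and a current-status answer will depend somewhat on where in the 1-4 week window the visit falls. The change does not align the item with the more-than-50% definition in section 6.0.

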#### 5.0 Inclusion and Exclusion Criteria/ Study Population

A chart review of all participants will be conducted at the initial visit for basic demographic information and co-morbidities. Inclusion criteria includes a history that is consistent with neurogenic cough (i.e. preceding viral illness, cough triggered by normal laryngeal functions such as voicing or laughing, environmental triggers such as perfume or noxious odors, etc.), exclusion of other well-known etiologies of cough and age  $\geq 18$  years. As part of the standard of care at our institution, patients are not treated for neurogenic cough until other etiologies of cough are excluded. Therefore, no funding for this study will be used in the evaluation of gastrointestinal reflux disease (GERD), pulmonary disease, or upper airway cough syndrome, as this is done routinely prior to diagnosis of neurogenic cough. All of our patients prior to enrollment in this study will have normal pulmonary function testing performed since their cough started, and a chest x-ray within the past six months. If a patient has known GERD or a history consistent with laryngopharyngeal reflux with a Reflux Symptom Index (RSI)  $> 13$  or Reflux Finding Score (RFS)  $> 11$ , then the patient will undergo evaluation for GERD including pH testing, EGD, high resolution manometry and/or esophagram. All of this standard of care testing for the evaluation of chronic cough will be done prior to patient enrollment and consent. Exclusion criteria will include patients on ACE inhibitors or Angiotensin II receptor blockers (ARBs), patients with uncontrolled obstructive sleep apnea, current smokers, and current neuromodulating medication use for chronic cough. If a patient presents on a neuromodulating medication, but is weaned off prior to the start of superior laryngeal nerve blocks, they may be included. This scenario may be encountered for those patients in whom a neuromodulating medication was not effective. Former smoking history will be permissible in the absence of pulmonary disease. A list of the inclusion and exclusion criteria are summarized in Table 1, shown below.

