## **10.0 Study Design / Methods**

Figure 2 depicts the flow diagram of the study design. Once patients have met inclusion and exclusion criteria (including undergoing all diagnostic testing for other potential causes of chronic cough) and have agreed to study participation, informed consent will be obtained and they will be randomized into two groups: treatment and placebo. This will be achieved using randomly-assorted, secured envelopes containing a card indicating whether the patient will be in the treatment or placebo group. This will be unveiled immediately to the provider administering the first injection, but remain unknown to the subject. There will be 25 "Treatment" and 25 "Placebo" cards within the 50, individually-secured envelopes. On initial visit, prior to the injection, patients will first undergo nasal laryngoscopy as part of standard of care. If there is any vocal fold weakness seen on scope examination or if there is a unilateral trigger point identified, then the first injection will start on the side of the suspected neuropathy. If there is no evidence of neuropathy on examination, we will start with a left-sided injection. Injections will be standardized to 2 mL of a 1:1 triamcinolone 40mg: 1% lidocaine with 1:200,000 epinephrine. Injection syringe will be brought into room by the physician in an opaque box and placed behind patient so they cannot view the syringe prior to injection. During the injection, a paper "shield" will be held under the patient's chin by an assistant and they will be asked to close their eyes so that they are not able to view the syringe during injection. This is necessary as steroid possesses a white color as compared to clear saline. The practitioner is not blinded so that proper drawing back on the syringe is not compromised to avoid intravascular or airway injection.

[figure not shown]

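### The readable text schedules the LCQ, the primary outcome measure, only at follow-up visits, so the planned change from before treatment cannot be derived under the schedule as written

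*Combined protocol and SAP*

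**What the plan says.** **Role of the LCQ.** Section 4.0 lists three measures of cough improvement and then ranks them: "Due to its validation, the LCQ will be the primary outcome measure". Section 10.0 repeats that ranking.

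**Analysis.** Section 12.0 states: "Changes in Leicester Cough Questionnaire scores, both global and specific domains (physical, psychological and social), will be analyzed via a linear regression model". The arms are afterwards compared by a two-sample t-test. Baseline LCQ is not named as a covariate.

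**Timing.** The only timing is in Section 10.0, in the text after the Figure 3 caption: "At each follow up visit, patients will provide a dichotomous answer (Yes or No) if they experienced improvement in cough". The next sentence but one-clause continuation of that visit list reads: "They will also fill out the Leicester Cough Questionnaire (LCQ), a validated 19-question quality of life survey for chronic cough".

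**Before injection 1.** Section 5.0 says: "A chart review of all participants will be conducted at the initial visit for basic demographic information and co-morbidities". Section 10.0 adds consent, randomisation by envelope, and then: "On initial visit, prior to the injection, patients will first undergo nasal laryngoscopy as part of standard of care". Neither section mentions an LCQ.

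**Other references to a baseline.** Section 10.0, after the Figure 2 caption, ties the side of injection 2 to whether "cough has improved by greater than or equal to 50% compared to baseline". No instrument or time is given for that baseline. The visual analogue scale in the patient log is completed daily after each injection, so it has no scheduled pre-injection value either.

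**The concern.** A change score needs a starting value, and the written schedule does not provide one. A site that follows the text literally would collect its first LCQ 1 to 4 weeks after injection 1, when any effect of that injection may already be present.

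A pre-treatment score cannot be collected after dosing. Each patient injected without one is permanently lost to the planned change analysis. The quality-of-life part of Aim 1a, which asks whether treated patients report improvement, depends on that change.

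**Working it through.** This is mainly a check of the schedule against the analysis. The plan's only sample-size figure, 18 per group in Section 6.0, concerns a dichotomous outcome (70% against 25%) and does not bear on the point. It does reproduce: reading the 80% as power and assuming two-sided 0.05, the arcsine formula gives 17.95, so 18, and the pooled-variance formula gives 19.

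**Step 1. LCQ time points in the readable text**

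| Stage | Described content | LCQ stated? |
|---|---|---|
| Initial visit (5.0) | Chart review: demographics, co-morbidities | No |
| Before injection 1 (10.0) | Consent, envelope, nasal laryngoscopy | No |
| After each injection (10.0) | Daily visual analogue log | No |
| Each follow-up visit (10.0) | Yes/no improvement, duration, LCQ | Yes |

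**Step 2. Which changes can be formed.** Let Y0 be the LCQ before injection 1, and Y1 and Y2 the scores at the follow-up visits after injections 1 and 2. Then

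Y2 − Y0 = (Y1 − Y0) + (Y2 − Y1).

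Without Y0, only Y2 − Y1 is available, and the gain reached by visit 1 drops out. The three-month contact does not help, because it also comes after injection 1. Section 2.0 reports that in the institution's own series the largest difference followed the initial injection. That was on a 0–10 severity scale, not the LCQ, so it is indirect evidence that the omitted part could be the larger one.

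**Step 3. Who has Y2 − Y1.** Section 10.0 ends enrolment for a patient who reports 0/10 severity after injection 1. Such a patient has no second injection and no Y2. The fallback change is therefore undefined for the best responders, possibly in unequal numbers by arm.

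**Step 4. Follow-up scores alone.** Randomisation makes the expected Y0 equal in both arms, so the arm difference in follow-up LCQ estimates the treatment effect without bias from the absent baseline. The plan's rules on out-of-window visits and early completion are separate matters. This comparison cannot give a within-arm change or adjust for chance imbalance with 25 per arm.

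**Step 5. Precision.** Assume equal SDs at both times and baseline to follow-up correlation r. The documents give no r. The relative variance of the arm difference is 1 for follow-up only, 2(1 − r) for change scores, and 1 − r² for baseline-adjusted regression.

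| r | Follow-up-only ÷ adjusted, 1/(1 − r²) | Follow-up-only ÷ change, 1/[2(1 − r)] |
|---|---|---|
| 0.3 | 1/0.91 = 1.10 | 1/1.4 = 0.71 |
| 0.5 | 1/0.75 = 1.33 | 1/1.0 = 1.00 |
| 0.7 | 1/0.51 = 1.96 | 1/0.6 = 1.67 |

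With 25 per arm, two-sided 0.05 and 80% power, the detectable difference on follow-up scores alone is (1.960 + 0.842) × √(2/25) = 0.79 SD. Multiplying by √[2(1 − r)] gives 0.94, 0.79 and 0.61 SD for change scores at r = 0.3, 0.5 and 0.7. Multiplying by √(1 − r²) gives 0.76, 0.69 and 0.57 SD for adjusted regression.

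**The case against.** **Figure 2 may contain the missing assessment.** Section 10.0 refers to it as the study flow diagram, and it was not available for this check. This stands. The point is limited to the readable text, and nobody can conclude from it that the plan as a whole has no baseline LCQ.

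**A baseline was probably intended.** An analysis of changes, and a rule that refers to baseline, both presuppose one. That makes an omission from the schedule more likely than a decision to skip it. An unwritten intention still gives clinic staff no instruction.

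**The treatment comparison survives.** A reader might infer that the primary comparison is lost altogether. The documents do not support that: allocation is randomised 25 to 25, and follow-up LCQ can be compared between arms. Nor does all of Aim 1a fail, because the yes/no answer still addresses reported improvement in cough.

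**The precision loss depends on the comparator.** Section 12.0 names changes and a t-test, with no baseline covariate. Against simple change scores there is no loss at r = 0.5, and below that follow-up-only is the more precise. The range 1.33 to 1.96 applies only against baseline-adjusted regression.

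**Neuromodulator wean.** Section 5.0 says that a patient who presents on such a drug but is "weaned off prior to the start of superior laryngeal nerve blocks, they may be included". A reader might infer that baseline could be on-drug and follow-up off-drug. Current use is an exclusion in Table 1, and Section 9.0 does not allow consent to be completed until the criteria are met. An LCQ taken after consent should therefore be off-drug. The worry would apply only to a pre-consent score, which the documents do not describe.

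**Conclusion.** The point holds for the schedule as written in the text. The primary measure is analysed as a change, its only stated time points follow injection 1, and the change that remains omits the effect of injection 1 and is undefined for patients who finish early on full resolution.

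What is at risk is the planned LCQ change, the within-arm quality-of-life result and the ability to adjust for baseline. The randomised comparison of follow-up scores is not at risk from this gap. The precision figures are illustrations that rest on an assumed r and equal SDs, and the conclusion does not depend on them.

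The point should be settled before further patients are injected, because the score cannot be recovered afterwards. If Figure 2 shows a baseline LCQ, what remains is to reconcile text and figure and to state its timing relative to consent and the envelope.

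**What to change.** 1. In Section 10.0, state that the LCQ is completed at the initial visit after consent, before the allocation envelope is opened and before injection 1, and that this score is the baseline for all LCQ changes.
2. In Section 12.0, name that baseline score as a covariate in the LCQ regression.
3. Check Figure 2 and make it agree with the text.
4. State which measurement, taken when, is the baseline for the 50% improvement rule in Section 10.0, so that it is reconciled with the baseline assessment. The clinical rule itself is not in question here.

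The cost is one 19-item questionnaire per patient (50 in all) at a visit that already takes place, plus short additions to two sections. No sample-size figure changes.
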